11.1 Research Ethics Committee (REC) review and reports	
11.2 Peer review	
11.3 Indemnity	
12. DISSEMINATION POLICY	30
13. REFERENCES	31

ii. LIST OF ABBREVIATIONS

BCAA	Branched-chain amino acid
BCKDH	Branched-chain alpha-keto acid dehydrogenase
CI	Chief Investigator
CRF	Case Report Form
CSA	Cross-sectional area
CTIMP	Clinical Trial of Investigational Medicinal Product
GCP	Good Clinical Practice
GLP	Good laboratory practice
MHRA	Medicines and Healthcare products Regulatory Agency
PDC	Pyruvate dehydrogenase complex
PI	Principal Investigator
REC	Research Ethics Committee
SAE	Serious Adverse Event
SOP	Standard Operating Procedure
TMF	Trial Master File

iii. TRIAL SUMMARY

Trial Title	The impact of Acipimox and Salbutamol supplementation on the development of insulin resistance and anabolic resistance during forearm immobilization in healthy, young volunteers	
Short title	Forearm immobilization, metabolic health, and muscle loss	
Trial Design	Randomized, double-blind, placebo-controlled trial with three parallel groups	
Study category	Basic science study involving procedures with human participants	
Trial Participants	Young healthy recreationally active males and females	
Planned Sample Size	45	
Treatment duration	2 days of forearm immobilization plus drug or placebo ingestion	
Planned Trial Period	Minimally 12 days (screening, baseline metabolic test day, approximate 7 days waiting period, 2 days forearm immobilization), maximally 33 days (waiting period can be up to 4 weeks, depending on availability of the participant).	
Study sites	
Royal Devon & Exeter NHS Foundation Trust Clinical Research Facility (CRF) and Clinical Trials Pharmacy Activities: screening and consenting (CRF), forearm cast application and removal (CRF), metabolic testing (CRF), drug dispensing to study participants (Pharmacy)
 
Nutritional Physiology research laboratories St Luke's Campus, University of Exeter Activities: preparation of a standardised diet, plasma analyses. If required: screening and consenting, forearm cast application
	
	Objectives	Outcome Measures
Primary	Determine the impact of reduced muscle lipid availability and increased glycolytic flux on forearm glucose uptake during short-term forearm immobilization in healthy volunteers	Forearm glucose uptake
Secondary	Determine the impact of reduced muscle lipid availability and increased glycolytic flux on muscle protein synthesis, and forearm nutrient balance during short-term forearm immobilization in healthy volunteers	Postabsorptive and postprandial muscle protein synthesis Forearm branched-chain amino acid and fatty acid balance Forearm volume
Medication to be administered	Administered during the 2-day forearm immobilization period: Acipimox OR Salbutamol OR Placebo	
Formulation, Dose, Route of Administration	Acipimox, 250 mg, 4 times daily, oral administration Salbutamol, 4 mg, 4 times daily, oral administration	

	Placebo, no active ingredients, 4 times daily, oral administration
CTIMP? (yes/no)	No (confirmation from MHRA is included in this application)

iv. FUNDING AND SUPPORT IN KIND

FUNDER(S)	FINANCIAL AND NON FINANCIAL SUPPORT GIVEN
Wellcome Trust [name]	Sir Henry Wellcome Postdoctoral Fellowship to [name]
Sport and Health Sciences College of Life and Environmental Sciences University of Exeter [name]	

v. ROLE OF TRIAL SPONSOR AND FUNDER

This study is funded by a 4-year Sir Henry Wellcome Postdoctoral Fellowship to [name]. [name] and [name] were responsible for the study design. The University of Exeter acts as a sponsor for this study. [name] will be responsible for data collection and analysis, decision to publish, and preparation of manuscript(s).

The UK Policy Framework for Health & Social Care and Medicines for Human Use (Clinical Trials) Regulations and Amendment Regulations 2006 require that all health-related research has a sponsor and sets out the responsibilities of the sponsor. The sponsor takes overall responsibility for the initiation, management and financing (or arranging the financing) of the research and must satisfy itself that appropriate arrangements are in place for management, monitoring and reporting of research activity. It is recognised that the sponsor can delegate specific responsibilities to any other individual or organisation that is willing and able to accept them. However, any delegation of responsibilities to another party should be formally agreed and documented by the sponsor.

vii. Protocol contributors

[name] – protocol development and scientific critique

[name] – protocol development and scientific critique

[name] (medical collaborator) – protocol development and risk assessment

[name] – Lead statistician

[figure not shown]
[name] – MRI Imaging Lead

viii. KEY WORDS:

[figure not shown]
Immobilization, disuse, inactivity, atrophy, insulin resistance, muscle protein synthesis

ix. TRIAL FLOW CHART

Trial flow chart

Schematic overview metabolic test days

1 BACKGROUND

During the course of life, individuals experience multiple bouts of physical inactivity, i.e. muscle disuse. Such periods of for instance illness or injury, which necessitate a period of bed rest or limb immobilisation, lead to a decline in muscle mass of 0.5-0.6% per day [1]. Importantly, older individuals have been shown to have an impaired recovery following such periods of disuse, such that even following a progressive resistance training programme muscle fibre size remains ~11% lower than prior to disuse [2]. As such, the accumulation of such bouts of physical inactivity is thought to contribute substantially to the observed loss of muscle mass with ageing [3, 4]. The occurring muscle atrophy is for a large part due to an impaired muscle protein synthetic response to food ingestion, termed anabolic resistance, a decline which can be as much as 30-55% following short-term immobilisation [5, 6]. In parallel, periods of muscle disuse lead to a deterioration of metabolic health by inducing substantial insulin resistance of glucose metabolism in skeletal muscle tissue. Indeed, following 7 days of muscle disuse, peripheral insulin sensitivity has been shown to decrease by 30-40% [7, 8]. By means of comparison, such a decline in insulin sensitivity is similar to the difference between a normal glucose-tolerant individual and a patient with type 2 diabetes [9], and is equivalent to a decline that is observed following 30–40 years of aging [10, 11]. Importantly, as the decline in muscle mass, strength, and insulin resistance have been shown to be good proxy markers for patient outcomes following hospitalization [12], it is highly important to attenuate or prevent this functional and metabolic decline. To design targeted intervention strategies, insight in the mechanisms underlying muscle disuse atrophy needs to be gained.

Previous work has shown that aberrant muscle fat metabolism is associated with insulin resistance [13]. More specifically, [name] recently showed that acute lipid infusion, known to induce insulin resistance, simultaneously induces anabolic resistance [14]. Indeed, there are changes in muscle lipid metabolism following 5-7 days of muscle disuse [7, 15], with overt muscle lipid accumulation after 28 days of bed-rest [16] or limb immobilisation [17], suggesting perturbed IMCL turnover may also play a major part of the physiological dysregulation associated with decreased physical activity levels. However, as the development of insulin resistance and anabolic resistance precedes overt skeletal muscle lipid accumulation, it is unclear if perturbed fat metabolism is involved in the development of insulin resistance and anabolic resistance during disuse.

At present, despite decades of physical inactivity research, the causes of disuse-induced insulin and anabolic resistance are still not known. Moreover, we simply do not know whether disturbances in muscle fuel availability and integration can explain the development of insulin resistance and anabolic resistance with muscle disuse. Importantly, if the development of insulin resistance and anabolic resistance can be attenuated or even prevented, this likely has a substantial positive effect on muscle mass retention during disuse. In other words, it will take shorter to get full recovery of muscle mass and muscle strength. Currently, the loss of muscle mass and strength results in protracted loss of function and increased cost on the NHS and Social care. This study will help us to understand how this atrophy occurs. This study will also determine if simple pharmacological interventions are a suitable intervention to prevent muscle loss over the first few days of muscle disuse.

2 RATIONALE

We hypothesize that muscle disuse alters intramuscular glucose and fatty acid metabolism, and their interaction, which consequently leads to decreases in insulin sensitivity and anabolic sensitivity. The primary aim of this study is therefore to determine the impact of reduced muscle lipid availability and increased glycolytic flux on forearm glucose uptake during short-term forearm immobilization in healthy volunteers. A secondary aim is to assess whether these simple pharmacological interventions have an impact on muscle mass loss during the first few days of immobilization; a critical period in a range of clinical scenarios, but one where we still do not know the mechanisms underpinning muscle loss.

We will perform a randomized, double-blind, placebo-controlled study in healthy, young volunteers that will directly characterise the metabolic status of inactive muscle tissue in situations of altered substrate availability. In order to unravel the underlying mechanisms and capture metabolic changes, it is crucial to study the muscle immediately after the onset of insulin resistance. Therefore, participants will undergo 2 days of forearm cast immobilisation, combined with fully-controlled nutritional intake. Prior to and immediately following immobilisation, a metabolic test day will be performed using the AV-V forearm balance technique combined with stable isotope amino acid infusion to quantify muscle glucose uptake (i.e. insulin sensitivity, the primary outcome measure), muscle protein synthesis and breakdown, as well as fatty acid and BCAA balance in the postabsorptive state and during a 3h hyperinsulinaemic-euglycaemic-hyperaminoacidaemic clamp. This clamp will be used as the hyperinsulinaemic-euglycaemic clamp (golden standard for measuring insulin sensitivity) is associated with hypoaminoacidaemia [18], which likely impacts on muscle protein synthesis [19]. By clamping glucose and amino acid concentrations, glucose uptake and muscle protein synthesis can be quantified under steady-state conditions while insulin concentrations are controlled for.

The following interventions will be used to alter muscle substrate availability in a randomised, double-blind, placebo-controlled study with a parallel-group design:

1. Placebo
2. Acipimox, an anti-lipolytic agent which decreases circulating lipids, inhibits intramuscular lipid accumulation and thereby reduces lipid supply to the mitochondria [20].
3. Salbutamol, a selective β_2 -agonist. Beta2-agonists have been shown to stimulate glycogenolysis and glycolytic flux [21], and exert a hypertrophic effect [22] by increasing muscle protein synthesis and decreasing proteolysis [23, 24].

Our protocol combines the arteriovenous-venous forearm balance technique with stable isotope tracer infusion under hyperinsulinaemic-euglycaemic conditions prior to and following 2 days of forearm immobilization under conditions of altered substrate availability. As such, this study will simultaneously determine the impact of muscle disuse on insulin sensitivity and muscle protein synthesis, and thereby gain crucial insight in the role of these processes, and their interaction, in inactivity-induced muscle loss. It will also determine if simple pharmacological interventions are capable of preventing muscle loss over the first few days of muscle disuse; a critical period in a range of clinical scenarios, but one where we still do not know the mechanisms underpinning muscle loss.

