The acipimox drug may cause some mild-moderate side effects in approximately 2 out-of 10 people. These side effects can include: skin rash; red 'flushed' skin; itching; sensations of hot skin. Less common effects include stomach pain and weakness. The salbutamol drug may cause mild-moderate side effects in approximately 1 out-of 10 people. These side effects can include fine tremor ('shaking', especially of the hands), headache, dizziness, and nausea. Less common side effects can include arrhythmias, low blood pressure, and muscle pain. These reactions usually disappear after 3 days, and failure of symptom reversal in a standard setting normally involves a participant being asked to stop taking the drug. Since participants in the current study are healthy volunteers who will only be taking the drugs for 2 days, no persistent side effects are expected. A clinical doctor ([name]) will be available for advice throughout the study.

Limb immobilization is a model routinely used to study muscle atrophy in humans, and our previous studies (Dirks et al. 2014 *Acta Physiol*, Dirks et al. 2016 *Acta Physiol*, Wall et al. 2013 *J Clin Endocrinol Metab*, Wall et al. 2014 *Acta Physiol*, Wall and Dirks et al. 2016 *AJP Endo Metab*) have used 3-14 days of forearm and leg immobilization in >100 healthy young volunteers without any problems. Forearm immobilization may lead to psychological limitations of having one arm in a cast. During the 2-day immobilization period, participants will likely experience difficulties in performing their daily activities due to only being able to use one arm. A sling will be provided to wear during the day, and a waterproof cover to protect the cast during showering. Any loss of muscle mass and strength that may occur will likely be smaller than 1%, and will restore quickly upon remobilization due to the inclusion of healthy young volunteers.

There will be a time burden on the participant, for which they will receive recompense. The time burden will be spread over a period of around 1.5 weeks, and they will only be required to visit the laboratory for a total of 4 visits. The largest cumulative time burden will be that required to complete the two metabolic test days, approximately 6.5 hours per day.

During the two days of forearm immobilization, participants will be asked to consume a controlled diet and nothing else. Because this diet will be calculated per participant to ensure energy-balanced

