5.5 Trial procedures

Please refer to page 11 for trial flow chart and schematic of the metabolic test days. The trial procedures are described below:

Screening visit (visit 1):

- Firstly, participants will be asked to meet the investigator so that the study can be explained to them in detail, and it is clear what they can expect from the research team and what will be expected of them. Assuming they are happy with what has been discussed, they will then provide written consent. Subsequently, they will complete a medical screening questionnaire and have their height, weight, body composition (Bodpod), and blood pressure measured.
- Participant's caloric requirements will be calculated by estimating Resting Metabolic Rate via the Henry equation, and then multiplying this value by an activity factor derived from the International Physical Activity Questionnaire (IPAQ) questionnaire.
- Forearm volume will be measured via anthropometry.
- Participants will be asked for any allergies or intolerances to ensure they can eat everything they will receive as part of the standardized diet.
- Participants will be provided with a food diary to record their habitual dietary intake for 3 consecutive days, including 2 week days and 1 weekend day.

Baseline metabolic test day (visit 2):

- Approximately 1 week prior to casting, at 8 AM, participants will visit the Clinical Research Facility at the Royal Devon & Exeter NHS Foundation Trust in an overnight fasted state for a metabolic test day.
- The following cannulas will be inserted by a trained research nurse: 1) retrogradely into a deep antecubital vein (draining the muscle bed) of the non-immobilised arm, 2) retrogradely into a superficial dorsal hand vein of the to-be-immobilised hand, and 3) anterogradely into an antecubital vein in the elbow of the to-be-immobilised arm for infusion of insulin, glucose, amino acids, and stable isotope amino acids. The cannulated hand will be placed into a hand-warming unit (air temperature 55°C) to arterialize the venous drainage of the hand.
- After insertion of all cannulas, a primed, continuous stable isotope infusion of L-[ring-²H₅]-phenylalanine (prime: 0.5 mg·kg⁻¹, infusion 0.5 mg·kg⁻¹·h⁻¹) will be started with participants in a supine position. Using this tracer approach we will be able to calculate muscle protein synthesis and plasma leucine oxidation.

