9.3.3 Secondary outcome analysis

Secondary outcome measures include postabsorptive and postprandial muscle protein synthesis, and forearm branched-chain amino acid and fatty acid balance. These data will be analysed in the same way as the primary outcome described above.

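### The aim of determining whether the drugs prevent muscle loss is not supported by the 2-day design as written, and the promised protein breakdown measure is missing from the outcomes and analysis

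*Combined protocol and SAP*

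**What the plan says.** **The muscle-loss aim.** The Rationale (section 2) states: "It will also determine if simple pharmacological interventions are capable of preventing muscle loss over the first few days of muscle disuse". The closing paragraph of the Background makes a similar statement. Earlier in the Rationale, an effect of the drugs on loss of muscle mass is called a secondary aim. The formal secondary objective (headed 3.2) covers protein synthesis and forearm nutrient balance and does not mention muscle mass.

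**The expected loss.** The Background says that periods of disuse "lead to a decline in muscle mass of 0.5-0.6% per day". The trial summary gives the exposure as "2 days of forearm immobilization plus drug or placebo ingestion". The risk section (section 3) says: "Any loss of muscle mass and strength that may occur will likely be smaller than 1" per cent. The Rationale ties the short exposure to studying muscle just after insulin resistance sets in, not to atrophy.

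**The size measure.** Forearm volume is a secondary outcome (3.4), and the table in 3.5 places the secondary outcomes on the metabolic test days. In section 5.5 the only entry is under the screening visit: "Forearm volume will be measured via anthropometry". Section 9.1 powers the trial on forearm glucose uptake alone. Section 9.3.3 omits volume: "Secondary outcome measures include postabsorptive and postprandial muscle protein synthesis, and forearm branched-chain amino acid and fatty acid balance".

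**Breakdown.** The Rationale says the test days will quantify "muscle protein synthesis and breakdown, as well as fatty acid and BCAA balance", and says beta2-agonists act "by increasing muscle protein synthesis and decreasing proteolysis"; section 7 repeats that mechanism for Salbutamol. Breakdown and net phenylalanine balance do not appear in 3.2, 3.4, 3.5 or 9.3.3.

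**The concern.** A claim that the trial will determine whether a drug prevents muscle loss needs three things: a loss large enough to see, a measure taken before and after it, and an analysis sized for it. The text supplies none of these clearly. If forearm volume is nevertheless measured after casting, a null result could be taken as evidence that the drugs do not spare muscle, and a positive one would be hard to trust.

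The design does collect most of what is needed to study early protein turnover: arterialised and deep-venous samples, blood flow and a phenylalanine tracer. Leaving breakdown and net phenylalanine balance out of the outcomes means that the proteolysis half of the stated beta2-agonist mechanism has no direct prespecified endpoint. Any later breakdown result would be a post hoc choice. It might not be computable at all, because section 5.8 lists phenylalanine enrichment but not concentration.

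**Working it through.** **1. The plan's own sample size (section 9.1).** Two-sample t-test, noncentral t, two-sided 5%, 80% power.
- Acipimox vs placebo: d = 13/8 = 1.625, giving n = 8 per group (power 0.856).
- Salbutamol vs placebo: pooled SD = √((8² + 6²)/2) = 7.07; d = (13 − 4.3)/7.07 = 1.23, giving n = 12 per group (power 0.821).
- Dropout: 12/(1 − 0.20) = 15 per group; 3 × 15 = 45.

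The stated figures reproduce exactly. They concern glucose uptake only.

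**2. Expected loss.** 2 days × 0.5-0.6% per day (Background) = 1.0-1.2%. The risk section expects less than 1%. The larger figure is used below, which favours the plan.

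**3. What 12 per group can detect.** Solving the same t-test at n = 12 per group for 80% power gives d = 1.197. A drug that prevents the whole loss creates a between-group difference equal to that loss, so the largest tolerable SD of the percentage change is:
- 1.0/1.197 = 0.84%
- 1.2/1.197 = 1.00%

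If a drug prevented 66% of the loss (the attenuation assumed for Salbutamol on glucose uptake), the limits fall to 0.66 × 0.84 = 0.55% and 0.66 × 1.00 = 0.66%.

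**4. Power for complete prevention.** The documents give no SD for change in forearm volume, so every SD here is an assumption.

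| Assumed SD of change | Power, 1.0% loss | Power, 1.2% loss | n per group for 80% power |
|---|---|---|---|
| 0.8% | 83% | 94% | 12 / 9 |
| 1% | 65% | 80% | 17 / 12 |
| 2% | 22% | 29% | 64 / 45 |
| 3% | 12% | 16% | 143 / 100 |

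At SD 2% the smallest difference detectable with 80% power is 1.197 × 2 = 2.4%; at SD 3% it is 1.197 × 3 = 3.6%. Both are at least twice the whole expected loss.

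These figures carry no multiplicity adjustment. Section 9.3.2 names a Bonferroni post-hoc test. If it covered three pairwise comparisons (0.05/3 = 0.0167 each), the largest tolerable SD would be 0.71-0.85%, and power at SD 2% would be 11-15%.

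**5. Breakdown, side by side.** Samples, Doppler flow and tracer are specified in 5.5, and enrichment is specified in 5.8. The Rationale promises breakdown. The sentence in 5.5 on what the tracer yields names protein synthesis and leucine oxidation only. No objective, outcome, endpoint table or analysis section carries breakdown forward.

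**6. Which arm.** Section 5.5 (visit 2) puts the deep-venous sampling cannula in the non-immobilised arm, and visit 4 repeats that test day. Read literally, no forearm balance, including the primary outcome, would come from the casted forearm.

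**The case against.** The strongest reply is that the muscle-loss sentences are background narrative. The null hypothesis, sample size and formal objectives concern glucose uptake, protein synthesis and nutrient balance; section 7 calls this a basic physiology study; no power is claimed for volume. That stands as a description of the formal objectives, and it limits the seriousness of the point. It does not remove the conflict, because the Rationale itself names muscle mass loss as a secondary aim and forearm volume is a listed outcome.

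A reader might also infer more than the documents support:

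- **That an effect on muscle size could not be detected at all, so a null result is empty and a positive one is noise.** This depends on an SD that the documents do not give. At 0.8%, complete prevention has 83-94% power. The supportable statement is that the aim is unpowered and would be unreliable unless the measure is very precise.
- **That the size measure is whole-forearm volume, including bone, skin and fat.** The anthropometric method is not described. Section 9.3.1 calls the variable forearm muscle volume, and an imaging lead is listed among the contributors. No imaging appears in the procedures text, so neither reading can be confirmed.
- **That net balance is left out, so a drug that lowers breakdown would look inactive.** Section 5.5 plans forearm amino acid balance, and BCAA balance is a listed and analysed outcome that lower proteolysis would be expected to affect. It is less specific, because BCAAs can be oxidised. The gap is breakdown and net phenylalanine balance.

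**Conclusion.** The concern holds in this form: the stated aim of determining whether the drugs prevent muscle loss is not supported by the design as written. The expected loss is about 1%. The one size outcome is scheduled in the procedures only at screening, is unpowered, and is absent from the analysis section. Complete prevention is detectable with 80% power only if the SD of change is at most 0.84-1.00%. That threshold rests on 12 completers per group, a two-sided 5% t-test and no multiplicity adjustment; the power figures rest in addition on the assumed SDs.

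The omission of breakdown and net phenylalanine balance is an inconsistency between the Rationale and the outcome and analysis sections. Adding them would not rescue the muscle-loss claim: flux measured after 2 days informs mechanism and does not show that loss was prevented. The 2-day duration is not at fault for the insulin-resistance question it was chosen to answer, and the primary sample size is not challenged here.

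**What to change.** 1. **Aim (sections 1 and 2).** Replace the statements about determining prevention of muscle loss with determining the effect on forearm muscle protein synthesis, breakdown and net balance. State that any change in forearm volume is descriptive, reported as an estimate with confidence interval, and that no conclusion about preventing muscle loss will be drawn from it. If volume is to be reported as a change, bring the visit schedule in 5.5 into line with the table in 3.5.
2. **Outcomes (3.4, 3.5, 9.3.3, 5.8).** Add postabsorptive and clamp-period muscle protein breakdown and net phenylalanine balance as secondary outcomes, analysed like synthesis. List phenylalanine concentration in the arterialised and deep-venous samples in 5.8. Say that these results will be interpreted as mechanism.
3. **Cannula site (5.5).** Reconcile the stated arm for the deep-venous cannula with the intention to measure the immobilised forearm, since every balance outcome depends on it.

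The cost is wording, a more modest stated aim, and possibly one extra concentration readout on samples already drawn. No additional blood, visits or participants are needed.
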